1.0 PROTOCOL SUMMARY AND/OR SCHEMA

This study will compare the effectiveness of autologous blood patch injection (ABPI) versus the BioSentry (formerly known as Bio-Seal) hydrogel Tract Plug (developed by Angiotech, Vancouver British Columbia) in reducing the rate of iatrogenic pneumothoraces when used in routine image guided lung biopsy procedures involving passage through aerated lungs. Both techniques are within the current standard of care in our institution. This involves the very last step of a lung biopsy which is removal of introducer needle. Patients who fulfill inclusion criteria will be randomized to one of two arms of the introducer needle removal technique. The patients will then be monitored in the post operative period for at least two hours with chest radiographs and any complications will be treated all as per standard of care practice. The vast majority of iatrogenic pneumothoraces from image guided lung biopsies occur within the first two hours post biopsy as determined by our own clinical experience [2] and confirmed by similar studies in the literature [3-5]. A follow up phone call (Appendix 20.4) to patients within two weeks after the lung biopsy is made to assess possible delayed pneumothoraces which are very rare and involve less than 1% of patients [2,3,5]. The phone call is not within standard of care. However any consequent treatments are within standard of care practice. We expect that less than 5 percent of all biopsies may end up being excluded during the procedure from intraprocedural complications precluding the use of a tract sealant.

The main objective is to determine non-inferiority of ABPI in the reduction of pneumothorax rate which is much cheaper to perform as opposed to BioSentry.

Potential candidates for this study will be recruited from patients referred to our Interventional Radiology service for lung biopsy.

2.1 OBJECTIVES AND SCIENTIFIC AIMS

Primary objective:

- To determine non-inferiority of ABPI when compared to BioSentry in reducing the rate of iatrogenic pneumothorax during the routine observation stay within 2 hours following image guided lung biopsy.

Secondary objective:

- To evaluate ABPI and BioSentry in reducing the rate of iatrogenic pneumothorax during the routine observation stay within 2 hours following image guided biopsy in a per-protocol analysis.
- To evaluate ABPI and BioSentry in reducing the rate of chest tube placement for pneumothorax up to two weeks following lung biopsy.
- To evaluate ABPI and BioSentry in reducing the rate of delayed pneumothorax up to two weeks following lung biopsy.

3.0 BACKGROUND AND RATIONALE

Percutaneous needle biopsy of lung is a well accepted and accurate method of diagnosis of pulmonary nodules and masses (90 % sensitive; almost 100% specific for malignancy) [6-8]. The demand for percutaneous lung needle biopsies is on the rise given the rising incidence of lung cancer, increased detection of asymptomatic lung nodules on imaging and the need for tissue for new molecular diagnostics [9]. In 2012 IR service performed 1128 lung biopsies which resulted in 86 chest tube placements and consequent admissions (%7.2). The total number of lung biopsies has constantly increased over time at our institution. IR service currently performs around 100 lung biopsies each month. The most common complication of a percutaneous lung biopsy is pneumothorax [10] or lung collapse and is caused by air leaking out of the lung through needle puncture site on the visceral pleura once the needle is removed. This is determined clinically and is observed either on the final post procedure CT images or on the follow up chest radiographs performed within 2 hours of the procedure while the patient is still in the recovery room. The majority of iatrogenic pneumothoraces is small and managed conservatively but they may require intervention by either aspiration or placement of a chest tube which usually implies a hospital admission. Most large series report an incidence of 15-25% for iatrogenic pneumothorax, but in some studies, the rate can reach as high as 40% [10]. In our institution, the rate of post biopsy pneumothorax is estimated at 23% based on a study performed in 2004 which is close to the literature findings [1]. The risk of pneumothorax requiring intervention, chest tube placement and admission is smaller but nonetheless appreciable and reported risks range between 4% and 6% [10] similar to the rate we reported from our institution which is 6.8% [1]. There is no accurate method of predicting which patient will develop a pneumothorax or require chest tube placement although multiple factors such as chronic lung disease, small nodule size, increased depth from skin and needle gauge size have been shown to be contributing elements [1,11]. However, when these complications do occur, the psychological and economic burden can be significant. A study in 1998 by Gurley et al evaluated the cost of inpatient management of patients with chest tubes and found that the average total management costs amounted to \$3,950 which was \$2,261 more than that for outpatients

(\$1,689). The significant cost difference was found to be related primarily to the room charge, pharmacy charges, and the number of follow-up chest radiographs obtained during the inpatient hospital stay^[12]. In our institution where the semi-private rate for inpatient hospital stay per day of stay is 4,180\$, we expect these charges to be even higher reaching up to \$10,342 of added cost when compared to biopsy patients who did not require a chest tube or admission. Given the rising need for biopsies, the relatively high incidence of iatrogenic pneumothoraces which can be potentially life-threatening and the high cost this particular complication incurs on healthcare resources when requiring treatment, there is great interest in techniques that reduce the occurrence of iatrogenic pneumothoraces. One such technique is the injection of certain materials into the biopsy path to close the puncture site, thus physically preventing air from leaking out into the pleural cavity. These materials have ranged from saline, to autologous blood, to manufactured plugs with varying results. The most popular of these have been the autologous blood patch and more recently a manufactured hydrogel plug called BioSentry [13]

An autologous blood patch consists of using the patient's coagulated blood to seal the puncture site at the end of a lung biopsy. The earliest report of its potential role in decreasing the incidence of pneumothorax was in 1988 where it was used in a limited number of patients, and though the results were not statistically significant, it did show a decrease in pneumothorax rate from 34.1% to 28% and a decrease in chest tube insertion rate from 9% to 7.7% [14]. Since then multiple other studies have evaluated the usefulness of the blood patch technique. Lang et al. showed a significant reduction in pneumothorax rate from 47% to 9% (p<0.05) in a study in 2000, and most recently in 2013, a randomized clinical trial was published in American Journal of Roentgenology (AJR) supporting the use of ABPI, mainly in reducing the rate of chest tube placement and admission from 18% to 9% (p<0.05) and similarly showing a trend in the reduction of pneumothorax rate from 35% to 26% (p>0.05)[15,16]. Following that same rationale, manufactured plugs have also been developed in recent years toward the same purpose. One such material is the BioSentry hydrogel plug developed by Angiotech and approved by FDA. BioSentry is deployed at the visceral pleural puncture site through the introducer needle using a deploying device (Figure 1). It swells upon contact with moisture and seals the pleural puncture site. It is absorbed by the patient's body over time. A supportive study of BioSentry by Zaetta et al. demonstrated a significant reduction of pneumothorax rate from 31% to 18%, and also a reduction –albeit non-significant- in the chest tube insertion rate from 11% to 4% compared to an untreated control group [13]. In an observation at our institution between 2007 and 2009, 181 consecutive patients undergoing lung biopsy by the author received blood patch. The rates of pneumothorax and chest tube placement, 6.6% (12/181) and 1.1% (2/181) respectively, were significantly lower than our group historical averages. Both of these techniques -either ABPI or BioSentry - along with "no plugging" are routinely used during lung biopsy procedures performed in our institution. Although both ABPI and BioSentry techniques have been independently validated in reducing the rate of pneumothorax and chest tube placement compared to controls, no head-to-head comparison has been made as to the effectiveness of these two techniques to justify the use of one over the other. There is no measurable added cost related to use of ABPI since the nursing personnel used in acquiring and handling the blood specimens are also involved in the patients' procedural sedation and thus perform these services within the scope of the procedure. Up to two standard stock syringes and

needles are used, the costs of which are negligible and lumped into the procedural costs. In comparison, the cost of a BioSentry device ranges around 200\$ per device. Given the economic advantage of using ABPI in that it is almost free, it is of interest for us to prove that ABPI is at least as effective as manufactured plug in reducing pneumothorax and chest tube rates as they occur in our institution in order to justify its exclusive use.

4.1 OVERVIEW OF STUDY DESIGN/INTERVENTION

4.2 Design

This study will determine the rate of all pneumothoraces and those pneumothoraces requiring treatment following percutaneous lung biopsy in patients who have received ABPI or BioSentry at the end of the biopsy procedure. The data collected will be used to determine if there is equal effectiveness in the reduction of pneumothorax rates from both interventions.

4.3 Intervention

Patients with a focal lung lesion amenable to needle biopsy who meet initial inclusion criteria will be randomized and will report for their scheduled appointments as per standard practice. Once the patient arrives into the procedure room, the appropriate sealant technique will be prepared based on the assigned randomization arm. If the patient was randomized to the manufactured plug arm, the device will be made available at the start of the procedure. If the patient was randomized to the blood patch arm, then before the start of the procedure, phlebotomy will be performed, drawing 2-3 mL of the patient's blood into a labeled anticoagulant-free syringe which will be capped and left to clot in a cap-down position.

The specific anatomical site of the biopsy will be selected by the interventional radiologist. All standard protocol for lung biopsy will be followed routinely including NPO status, monitored sedation, and withholding of anticoagulation medications along with aspirin and clopidogrel bisulfate as per guidelines of MSKCC IR service. All biopsies will be performed using coaxial technique under CT guidance.

A limited CT scan of the lesion and adjacent lung parenchyma is acquired for biopsy planning. A biopsy path will be chosen to avoid pulmonary blebs, fissures, and pulmonary and superficial vessels, while the patient is positioned accordingly.

A biopsy path traversing at least 1.5 cm of aerated lung will be preferred so that an effective ABPI or BioSentry might be applied. Biopsies will be performed by any of the attending interventional radiologists or by an interventional radiology fellow under the direct supervision of an attending. A small sterile field is set. Local anesthesia will be used. An Angiotech 19-gauge introducer needle will be advanced into the corresponding lung with the needle tip at the near edge of the lesion. A 20-gauge automatic spring-loaded core biopsy gun (for example Temno, ACT) or a 20-22 Gauge FNA needle (for example Westcott) will be used to obtain core tissue and/or FNA samples. A cytotechnologist will be present on-site for all biopsies to assess adequacy of tissue samples as per standard of care.

Once the sample has been deemed adequate, and prior to removal of the guiding needle, the appropriate sealant technique will be delivered based on the patient's randomization arm.

If the patient was assigned to the ABPI group, a blood patch will be administered using the clotted blood in the syringe obtained at the beginning of the procedure. The guiding needle will be retracted up to 1.5-2 cm from the pleural surface, and the blood will be injected steadily and gently as the needle is pulled back out of the pleura. Injection will stop when the operator feels the needle is in subcutaneous tissues.

If the patient is assigned to BioSentry group, using the manufacturer's deployment device (Figure 1) the introducer needle is positioned so that the tip is at least 1.5 cm deep to the visceral pleura. The coaxial introducer needle hub will be prehydrated with a drop of saline, the BioSentry plug housing will be mated and locked to the hub and the plug will be deployed.

If during the biopsy procedure, there was onset of a pneumothorax before deployment of autologous or manufactured plug, or there was more than one pleural puncture, or passage through a fissure, a bleb, non aerated lung, the sealant may be administered if still technically feasible, and the decision will be at the discretion of the operator. If a coaxial system was not used, the sealant cannot be administered. These cases will be included in the primary intent-to-treat analysis, but excluded in a secondary per-protocol analysis:

- More than 1 needle pass through visceral pleura
- Passage of needle through pleural fissure, bleb, or bulla
- Passage of needle through consolidated or non-aerated lung
- Co-axial biopsy system not used
- Development of pneumothorax before deployment of BioSentry or ABPI
- Use of introducer needle larger than 19 gauge
- Needle length more than 15 cm

We expect that less than 5 percent of all biopsies may end up being excluded during the procedure from intraprocedural complications precluding the use of a tract sealant.

After the procedure, all patients will be transferred to the recovery unit where at least two chest radiographs will be obtained immediately and 2 hours after the procedure according to standard of care. Additional radiographs may be obtained if indicated according to standard of care.

The post procedure chest radiographs will be evaluated by the biopsy operator for the presence of pneumothorax which will appear as free air collection overlying the lung parenchyma inside the chest wall. A Pneumothorax is generated from air leaking from the needle puncture site into the visceral pleura. Patients with no or small stable asymptomatic pneumothoraces will be discharged.

A chest tube will be placed for patients with a large pneumothorax, patients with a pneumothorax that is increasing in size, or symptomatic patients with potentially any size pneumothorax on post procedure chest radiographs. Most patients who undergo chest tube placement will be admitted for overnight observation. Chest tubes will be removed when there is no longer an air leak and the radiographic appearance remains stable for 2 hours

with the chest tube clamped. This happens the next day of the biopsy for the majority of cases. Patients will be discharged home once the chest tube is removed. At the time of discharge all patients will be given contact information and will be asked to call back with any symptoms that might be related to delayed pneumothorax. In addition, patients who do not have a chest tube placed will be also followed up with a phone call by a member of IR service at one week checking for delayed pneumothorax (appendix 20.4). In case any of the study patients present with symptomatic or incidental delayed pneumothorax after being discharged, these patients' data will be captured for analysis. This phone call is the only part of this study which is not a part of standard of care however any consequent interventions based on the phone call are within standard of care practice.

All biopsy chest radiographs and CT images will be analyzed by the radiologist performing the procedure to identify emphysema (appendix 20.2.2) if present. The prescan images, as well as any recent chest CT studies, if available, will be examined in lung windows on the PACS workstation. The lung parenchyma surrounding the lesion and in the region of the biopsy needle course will be analyzed for emphysema, blebs and transfissural approach.

Pneumothorax (appendix 20.2.1) will be mainly defined based on post procedure chest x-rays. Any discernible pneumothorax on chest x-rays is considered a positive finding. Minuscule pneumothorax (a tiny film of air) which is sometimes seen on the last set of CT images of a biopsy procedure after the introducer needle is removed is not considered a positive finding. This is due to high sensitivity of CT imaging. Any pneumothorax larger than minuscule on CT images is considered a positive finding.

5.0 THERAPEUTIC/DIAGNOSTIC AGENTS

The BioSentry Biopsy Tract Plug (Angiotech Pharmaceuticals, Inc. Vancouver, Canada; Figure 1, Appendix 20.1), is a hydrogel based tract sealant which has been FDA approved to be used through standard Angiotech 19 gauge coaxial needles. It can be made currently available in stock for routine use during lung biopsy procedures.

An autologous blood patch injection (ABPI) consists of drawing 2-3 mL of the patient's blood prior to the procedure and leaving it in a sterile syringe to clot, then using the patient's coagulated blood to seal the puncture site at the end of a lung biopsy. This technique can be used through 19 gauge needles.

6.1 CRITERIA FOR SUBJECT ELIGIBILITY

6.2 Subject Inclusion Criteria

- ≥ 18 years of age
- Referred for CT guided biopsy of lung lesion
- Target lesion of any size
- Target lesion located 1.5 cm or more away from visceral pleura based on the needle path
- Skin thickness ≤ 7 cm (from skin to pleura)
- Needle path without transgression of pleural fissure, bleb, or bulla is possible
- Coaxial biopsy technique using Angiotech 19-Gauge introducer needle

- Needle length ≤15 cm

6.3 Subject Exclusion Criteria

- Preprocedural exclusion criteria
 - Passage through non-aerated lung or tissue
 - More than 1 biopsy on the same side requiring more than 1 pleural puncture
 - History of prior ipsilateral lung interventions including:
 - Chest tube placement
 - Surgery
 - Pleurodesis
 - Radiation treatment

7.0 RECRUITMENT PLAN

The subjects of this study will be identified and recruited by members of the Interventional Radiology service through referrals for lung biopsy. There will be no selection preferences based on age, gender, race, indication or target lesion characteristics. The patients will be selected initially based on the inclusion criteria outlined above and also based on appropriate clinical history as outlined in the exclusion criteria. This process will be conducted during the patient's visit to the interventional radiology clinic or in the inpatient unit prior to the patient's biopsy. The interventional radiologist performing the clinic evaluation or procedure consent will determine eligibility of the patient and discuss potential enrollment in the study. Subjects recruited as inpatients will be consented to the protocol and biopsy on the inpatient floor about an hour prior to the procedure. As these biopsies are not planned in advance, the time between ordering and performing the biopsy is minimal. The consenting professional will give ample time for discussion and questions.

All parameters related to the study are collected by treating IR physicians in Physicians Data Form for each patient (Appendix 20.3).

During the initial conversation between the investigator/research staff and the patient, the patient may be asked to provide certain health information that is necessary to the recruitment and enrollment process. The investigator/research staff may also review portions of their medical records at MSKCC in order to further assess eligibility. They will use the information provided by the patient and/or medical record to confirm that the patient is eligible and to contact the patient regarding study enrollment. If the patient turns out to be ineligible for the research study, the research staff will destroy all information collected on the patient during the initial conversation and medical records review, except for any information that must be maintained for screening log purposes.

In most cases, the initial contact with the prospective subject will be conducted either by the treatment team, investigator or the research staff working in consultation with the treatment team. The recruitment process outlined presents no more than minimal risk to the privacy of the patients who are screened and minimal PHI will be maintained as part of a screening log. For these reasons, we seek a (partial) limited waiver of authorization for the purposes of (1) reviewing medical records to identify potential research subjects and obtain information

relevant to the enrollment process; (2) conversing with patients regarding possible enrollment; (3) handling of PHI contained within those records and provided by the potential subjects; and (4) maintaining information in a screening log of patients approached (if applicable).

During a biopsy procedure, less than ideal conditions may occur such as outlined above that may affect clinical outcome. In this case deployment of blood patch or plug may still proceed at the performing physician's discretion, and the patient will be included in the intent-to-treat analysis.

The recruitment process outlined presents no more than minimal risk to the privacy of the patients who are screened and minimal PHI will be maintained in a secure database as part of a screening log. The screening log will be maintained in order to ensure that patients who do not wish to participate are not approached again.

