20.4 PHYSICIAN DATA FORM

Effect of Autologous Blood Patch Injection versus BioSentry hydrogel Tract Plug in the reduction of pneumothorax risk following lung biopsy procedures

1- Patient Demographics

MRN		Procedure date		/	/	
Last Name		Male	Female	DOB	/	/

2- Candidate for study Yes No

If no, please explain why or list/circle exclusion criteria #:

3- Consent obtained Yes No

4- Randomization # _____

5- Procedure parameters

Exclusion criteria

1. Passage through non-aerated lung or tissue OR Target lesion located LESS than 1.5 cm away from visceral pleura
2. Needle path transgressing pleural fissure or bleb
3. Coaxial technique not needed
4. Needle size 17 gauge
5. Prior ipsilateral lung interventions: biopsy, chest tube, surgery, radiation or pleurodesis

Target size (largest transverse diameter on reference image) _____ cm

Target depth (Needle path distance from pleura to outer edge of target) _____ cm

Lobe (please circle) RUL RML RLL LUL LLL

Position (please circle) Prone Other:

Type of biopsy (please circle) FNA Core Both

Number of biopsy samples FNA: Core:

6- Factors affecting outcome: Did you encounter (please circle)

More than 1 pleural puncture? Yes No

Passage through a fissure? Yes No

Complete passage through non aerated lung? Yes No

Passage through a bleb/bulla? Yes No

Usage of BARE needle WITHOUT coaxial system? Yes No

Intraprocedural pneumothorax? Yes No

Significant needle path hemorrhage within 2 cm of pleura? Yes No

7- Sealant technique used (please circle) Blood patch BioSentry None
 (Please note reason below)

8- Outcomes

Pneumothorax on CXR (please circle) Yes No

Pneumothorax - Second reader (please circle) Yes No

Chest tube placement (please circle) Yes No

Delayed complications (please circle) Yes No If Yes: _____

Notes:

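### No rule requires the per-protocol exclusion items to be recorded before the unmasked operator reads the films, so membership of that secondary analysis could be influenced by the outcome

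*Combined protocol and SAP*

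**What the plan says.** - **Who records.** Section 7.0: "All parameters related to the study are collected by treating IR physicians in Physicians Data Form for each patient (Appendix 20.3". (It points to Appendix 20.3; the form stands under 20.4.)
- **Who knows the arm.** Section 4.3: once the sample is adequate, "the appropriate sealant technique will be delivered based on the patient's randomization arm". The operator is therefore unmasked.
- **Who reads the films first.** Section 4.3: "The post procedure chest radiographs will be evaluated by the biopsy operator for the presence of pneumothorax".
- **What the conditions do.** Section 4.3 lists seven procedural conditions and says: "These cases will be included in the primary intent-to-treat analysis, but excluded in a secondary per-protocol analysis".
- **Where they are recorded.** Appendix 20.4, under "6- Factors affecting outcome: Did you encounter (please circle", has yes/no items for five of the seven: repeat puncture, fissure or bleb/bulla, non-aerated lung, no coaxial system, and intraprocedural pneumothorax. Introducer gauge appears only as a pre-procedure exclusion. Needle length is not on the form.
- **What else is on the form.** Item 8 holds "Pneumothorax on CXR (please circle) Yes No", "Pneumothorax - Second reader (please circle) Yes No", chest tube placement and delayed complications.
- **Masked review.** Section 10.0 provides a masked second reading and a third reader for disagreements, for chest radiographs only.
- **Another definition.** Section 14.0 restricts the secondary analysis to patients in whom a sealant was actually placed, and does not use the seven-condition list.

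**The concern.** One unmasked person delivers the assigned sealant, reads the radiographs and records the facts that decide whether the patient counts per protocol. The documents do not fix the order of the last two steps.

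Several items are image judgements, such as whether the needle crossed a fissure, a bleb or non-aerated lung. A pneumothorax prompts a search for its cause, and the title of item 6 invites one. The item on intraprocedural pneumothorax is closer still to the outcome: it does not ask whether the air appeared before or after the sealant was deployed, yet the Section 4.3 exclusion turns on exactly that.

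If a patient with a pneumothorax is more likely to have an exclusion condition circled, failures leave the per-protocol set selectively. If this happens more in the ABPI arm, the per-protocol comparison is biased towards non-inferiority. Readers of a non-inferiority trial usually look to the per-protocol result for support, because deviations can dilute a real difference under intent-to-treat.

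**Working it through.** **Inputs from Section 14.0.** BioSentry rate 20%, margin 10 percentage points, 276 per arm, one-sided 5%, boundaries -2.538 at half the information and -1.662 at the end.

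**Step 1: the plan's own figures.** For a fixed design, n = (1.645 + 1.282)² × 2 × 0.20 × 0.80 / 0.10² = 274.04, so 275 per arm. With the two boundaries and correlation √0.5 between looks, the overall one-sided error is 0.0500. At 276 per arm the drift is 0.10/√(0.32/276) = 2.937 and power is 90.0%. The plan's figures reproduce, and this point does not touch them.

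**Step 2: selective exclusion in the ABPI arm only.** Assume true rates of 30% and 20%, so ABPI sits exactly at the margin and any pass is false. Expected ABPI failures are 276 × 0.30 = 82.8. If a share f of them is excluded:

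- p_A = 0.30(1 − f)/(1 − 0.30f) and n_A = 276(1 − 0.30f)
- SE = √[p_A(1 − p_A)/n_A + 0.20 × 0.80/276]
- θ = [0.10 − (p_A − 0.20)]/SE
- false pass = 1 − Φ₂(2.538 − θ√0.5, 1.662 − θ; correlation √0.5)

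| f (assumed) | Failures removed | n_A | p_A | Difference (points) | θ | Per-protocol false pass |
|---|---|---|---|---|---|---|
| 0 | 0 | 276.0 | 30.0% | 10.0 | 0 | 5.0% |
| 2% | 1.7 | 274.3 | 29.6% | 9.6 | 0.115 | 6.3% |
| 5% | 4.1 | 271.9 | 28.9% | 8.9 | 0.292 | 8.8% |
| 10% | 8.3 | 267.7 | 27.8% | 7.8 | 0.594 | 14.6% |

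A two-look simulation gives 6.4%, 8.8% and 14.7%.

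**Step 3: the same share leaves both arms.** With f = 10% in each arm, p_B = 0.20 × 0.90/(1 − 0.20 × 0.10) = 18.4%. The difference is 27.8 − 18.4, about 9.5 points; θ = 0.147 and the false-pass rate is 6.7%. If equal numbers of failures, rather than equal shares, leave both arms, or if exclusion is at random, the rate does not move: a simulation using the final boundary alone gives 4.9% with or without 14 such exclusions per arm.

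**Step 4: both analyses together.** Removing ABPI failures moves the per-protocol statistic towards passing, so trials that falsely pass intent-to-treat also pass per protocol. The joint false-pass rate therefore equals the intent-to-treat rate. Simulation gives 5.0% to 5.1% at f = 2%, 5% and 10%.

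**Step 5: timing.** The form as a whole cannot be finished before the outcome is known, because item 8 includes the later second reading and delayed complications. Items 5 to 7 could be finished earlier. No section says that they must be, and none provides a time-stamp, a lock or masked adjudication for them.

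**The case against.** The strongest counter-argument is that Section 14.0 defines the secondary set by whether a sealant was placed. That is item 7, a fact settled in the procedure room before any recovery radiograph. Under that definition the judgements in item 6 hardly matter. This stands as far as it goes, but the Section 4.3 list is also current text, so the two must be reconciled before anyone can say which set applies.

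Second, several conditions are plain procedural facts (coaxial use, gauge, length, number of punctures), and the others could be rechecked on stored CT images. Section 16 also provides for source documents, data-quality reports and audits. This limits the room for bias. None of it is a check of per-protocol membership masked to arm and outcome, and Section 4.3 gives the reading for blebs and transfissural approach to the same operator.

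Third, the direction of any bias is assumed. Section 3.0 states an interest in justifying exclusive use of ABPI, but Section 9.0 says that preferences vary among practitioners. A uniform tilt towards ABPI is possible, not shown.

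Three stronger readings are tempting, and the documents do not support them:

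- A reader might infer that the exclusion items are in fact left open and failures removed afterwards. The form's layout and the missing timing rule show an opportunity, not a practice.
- A reader might infer that the non-inferiority conclusion depends on the per-protocol result. Section 2.1 lists it as a secondary objective and Section 14.0 as a secondary analysis; no section makes it a condition.
- A reader might take 15% as the trial's false-positive rate. Step 4 shows that the chance of both analyses falsely passing does not rise.

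**Conclusion.** The point holds as a minor safeguard gap confined to the secondary per-protocol analysis. The primary analysis keeps these patients (Sections 4.3, 13.0 and 14.0) and is unaffected.

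The per-protocol false-pass rate could rise from 5% to about 6%, 9% or 15% under one-sided exclusion of 2%, 5% or 10% of ABPI failures, and to about 7% if 10% of failures left both arms. What would be lost is the value of the per-protocol result as supporting evidence.

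These figures rest on assumed shares, on true rates at the margin, and on applying both of the plan's boundaries to the per-protocol analysis. Section 14.0 says the same method will be used but does not explicitly give that analysis an interim look. The risk is smaller if the sealant-placed definition governs.

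**What to change.** 1. **Section 14.0:** reconcile the Section 4.3 list with the sealant-placed definition and state one per-protocol set.
2. **Data form:** add actual introducer gauge and needle length as procedural facts. Record at deployment whether a pneumothorax was already present. Complete, time-stamp and lock items 5 to 7 at the end of the procedure, before the immediate radiograph is read.
3. **Corrections:** log later changes with a date and reason, and take per-protocol membership from the locked entries only.

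The cost is two form fields, a timed entry at deployment, a form rule and a short addition to Section 14.0, with no extra patients or image reads. It has to be in place while data are being collected; it cannot be added afterwards.

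Two limits remain. A genuine late correction would not change the per-protocol set. A pneumothorax already visible on the final CT, which Section 4.3 counts as positive when larger than minuscule, would still be known to the operator at the lock.
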